10.0 Safety Analyses

10.1 General Considerations

Safety analyses will be performed on the safety population for the Induction Period (SA1), the Re-Induction Period (SA2), the Maintenance Period (SA3) and SA-RES, SA-ALL154 population as defined in Section 4.0. In addition, safety summaries will be

performed on the safety analysis set for combined data from different periods (SA-IN2, SA-INMN, SA-IN2MN).

The standard safety analyses will include reporting of adverse events (AEs), adverse events of special interest (AESIs), laboratory, and vital signs measurements. Frequency tables and exposure adjusted event rate per 100 patient-years tables of subjects with treatment-emergent adverse events (TEAEs) by system organ class (SOC) and by preferred term (PT) as in the Medical Dictionary for Regulatory Activities (MedDRA) dictionary will be provided by treatment group. All continuous laboratory parameters and vital signs variables at each visit will also be summarized by treatment group. Frequency tables of subjects meeting criteria for potentially clinically important vital sign values and for potentially clinically important laboratory values will be provided by treatment group.

For safety analyses (such as analyses of laboratory and vital signs measurements) in the Induction Period, the baseline value is defined as the last available measurement before study drug administration for all subjects (including subjects who received placebo). For all other safety analyses, the baseline value is defined as the last available measurement before first administration of ABBV-154 for all subjects.

For the safety analysis, subjects are assigned to a treatment group based on the treatment actually received, regardless of the treatment randomized.

Missing safety data will not be imputed.

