The all ABBV-154 safety population (**SA-ALL154**) includes all subjects who received at least one dose of ABBV-154 in the Induction Period, or the Re-Induction Period, or the Maintenance Period.

The all ABBV-154 rescue safety population (**SA-RES**) includes all subjects who received at least one dose of ABBV-154 rescue therapy in the Maintenance Period.

The following safety populations are defined for safety analyses based on data from multiple study periods:

SA-IN2: all subjects who received at least one dose of ABBV-154 in both Induction Period and Re-Induction Period.

SA-INMN: all subjects who received at least one dose of ABBV-154 in either Induction Period or Re-Induction Period AND at least one dose of ABBV-154 in the Maintenance Period.

SA-IN2MN: all subjects who received at least one dose of ABBV-154 in the Induction Period AND at least one dose of ABBV-154 in the Re-Induction Period AND at least one dose of ABBV-154 in the Maintenance Period.

For the safety populations, subjects are assigned to a treatment group based on the "as treated" treatment group, regardless of the treatment randomized.

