10.2.1 Treatment-Emergent Adverse Events

Induction Period (SA1 population): TEAEs for the Induction Period are defined as events that begin either on or after the first dose of the study drug in the Induction Period and until (i) the first dose of study drug in the Re-Induction Period (if applicable), or (ii) until first dose of study drug in the Maintenance Period (if applicable), or (iii) within 70 days after the last dose administration of the study drug in the Induction Period, whichever is earlier.

Re-Induction Period (SA2 population): TEAEs for the Re-Induction Period are defined as events that begin either on or after the first dose of the study drug in the Re-Induction Period and until (i) first dose of study drug in the Maintenance Period (if applicable), or (ii) within 70 days after the last dose administration of the study drug in the Re-Induction Period, whichever is earlier.

Maintenance Period (SA3 population): TEAEs for the Maintenance Period are defined as events that begin either on or after the first dose of the study drug in the Maintenance Period and until (i) within 70 days after the last dose administration of the blinded study drug in the Maintenance Period, or (ii) initiation of ABBV-154 rescue therapy, whichever is earlier.

ABBV-154 Rescue Therapy (SA-RES population): TEAEs for the ABBV-154 rescue therapy are defined as events that begin either on or after the first dose of the ABBV-154 rescue therapy in the Maintenance Period and until 70 days after the last dose administration of the study drug in the Maintenance Period.

All ABBV-154 (SA-ALL154 population): TEAEs for "All ABBV-154" are defined as events that begin either on or after the first dose of ABBV-154 and within 70 days after the last dose of ABBV-154 in the study. Events that begin when subjects on Placebo will be not included.

Safety analyses from combined periods:

Induction Period + Re-Induction Period ABBV-154 (SA-IN2 population): TEAEs for "Induction Period + Re-Induction Period ABBV-154" (SA_IN2) are defined as events that begin either on or after the first dose of ABBV-154 in the Induction Period and until (i) first dose of study drug in the Maintenance Period (if applicable), or (ii) within 70 days after the last dose of study drug in the study, whichever is earlier.

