10.3 Analysis of Laboratory Data

Data collected from central and local laboratories, including additional laboratory testing due to an SAE, will be used in the analyses. Baseline values collected for SAE-related laboratory assessments on or before the first dose of study drug will be excluded. Data collected more than 70 days after the last dose of study drug of the analysis period (See Section [10.2.1](#)) for the corresponding analysis populations will be excluded.

The clinical laboratory tests defined in the protocol (e.g., hematology and clinical chemistry) will be summarized.

Analysis of Quantitative Laboratory Parameters

Each laboratory variable will be summarized at all time points (starting at baseline) with the number of observations, mean, standard deviation, median, minimum and maximum

for non-missing observations. The change from Baseline at each applicable post-baseline visit will be summarized for selected laboratory variables, with the number of observations, baseline mean, and visit mean. The mean, standard error, and 95% CI will be presented for the change from Baseline for each treatment group.

For each period, treatment group differences for the changes from baseline will be analyzed using a one-way Analysis of Variance (ANOVA) model with treatment as a fixed factor and 95% CI for treatment difference will be presented for selected laboratory parameters.

Shift Table Analyses

Changes in laboratory parameters will be tabulated using shift tables categorized as low, normal, or high based on the normal ranges of the laboratory used for each sample. A shift table summarizes shifts from baseline to minimum and maximum values (based on normal range) will be created. A similar shift table will be provided to summarize shifts from baseline to the final post-baseline value.

Potentially Clinically Significant Laboratory Values

The criteria for potentially clinically significant laboratory values will be determined by CTCAE criteria of Grade 3, Grade 4 and \geq Grade 3, with a grade worsening compared to baseline. Toxicity grading scale is based on National Cancer Institute Common Toxicity Criteria (NCI CTC) AE version 5.0. The number and percentage of subjects meeting the criteria for potentially clinically significant laboratory values will be summarized by treatment group. Listings of subject-level laboratory data will be provided for subjects meeting the criteria.

Assessment of Liver Elevations

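### Rescue safety set (SA-RES): laboratory and vital-sign change is measured from before the first ABBV-154 dose, while adverse events are counted from the first rescue dose

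*SAP*

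**What the plan says.** SAP 4.0 defines SA-RES as the set that "includes all subjects who received at least one dose of ABBV-154 rescue therapy in the Maintenance Period". SAP 10.1 names it among the sets for safety analysis: "the Maintenance Period (SA3) and SA-RES, SA-ALL154 population as defined in Section 4.0". The same section gives two baselines for measurements. In the Induction Period it is the last value before study drug. Otherwise: "For all other safety analyses, the baseline value is defined as the last available measurement before first administration of ABBV-154 for all subjects". No other section gives SA-RES a baseline of its own.

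Four outputs use that baseline:

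- laboratory change from baseline (SAP 10.3);
- laboratory shift tables (SAP 10.3): "A shift table summarizes shifts from baseline to minimum and maximum values (based on normal range) will be created", with a similar table for the final value;
- potentially clinically significant laboratory values (SAP 10.3), which need CTCAE Grade 3 or higher "with a grade worsening compared to baseline";
- vital-sign change from baseline (SAP 10.4).

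Adverse events follow a different clock. SAP 10.2.1 counts for SA-RES "events that begin either on or after the first dose of the ABBV-154 rescue therapy in the Maintenance Period". It closes the Maintenance set (SA3) 70 days after the last blinded dose or at "initiation of ABBV-154 rescue therapy, whichever is earlier".

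For laboratory and vital-sign data, SAP 10.3 and 10.4 state when the window ends (70 days after the last dose of the analysis period) and refer to 10.2.1. Neither states when it starts.

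**The concern.** SA-RES is useful if it shows what follows rescue. Cumulative experience since first exposure is already covered by SA-ALL154, which runs from the first ABBV-154 dose to 70 days after the last one, rescue included. Under the present rule the SA-RES adverse-event tables start at rescue, while the laboratory and vital-sign tables beside them start up to a year or more earlier, at a point that differs by route of entry.

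A laboratory value can then enter the rescue table as a worsening although nothing changed after the rescue dose, and a value that did become abnormal after it can be left out. SA-RES has no control group, so no second column would show a reader that this has happened.

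**Working it through.** The SAP gives no figure to reproduce. The check has two parts: how far the baseline lies from rescue, and how the counting rule treats typical grade patterns.

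**1. Distance from baseline to rescue.** Inputs: Induction and Re-Induction last 12 weeks each (SAP 2.2). Rescue is possible from Maintenance Week 4 (SAP 2.2; Protocol 5.4). The last study-drug dose is at Maintenance Week 38 (SAP 2.2; Protocol 4.1 and 5.7). Placebo induction responders receive ABBV-154 from Maintenance Week 0 (SAP 2.2). Visits are taken as on schedule.

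Weeks from first ABBV-154 dose to rescue = weeks from first ABBV-154 dose to Maintenance Day 1 + Maintenance week of rescue.

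| Route into Maintenance | Weeks before Maintenance | Rescue at Week 4 | Rescue at Week 38 |
|---|---|---|---|
| ABBV-154 in Induction, responder | 12 | 16 | 50 |
| Placebo in Induction, responder after Re-Induction | 12 | 16 | 50 |
| ABBV-154 in Induction, responder after Re-Induction | 24 | 28 | 62 |
| Placebo in Induction, responder | 0 | 4 | 38 |

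Protocol 5.4 describes rescue through Week 40. On that reading the upper limits are 52, 52, 64 and 40. On either reading the shortest gap is 4 weeks, so no planned route has a baseline at rescue.

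**2. The counting rule.** A value is counted if the highest grade after rescue is at least 3 and exceeds the baseline grade. Patterns are grade before first ABBV-154 / last before rescue / highest after rescue.

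| Pattern | Meaning | SAP baseline | Baseline reset at rescue |
|---|---|---|---|
| 0/3/3 | present before rescue, persists | counted | not counted |
| 0/4/3 | improving, still Grade 3 | counted | not counted |
| 0/0/3 | new after rescue | counted | counted |
| 0/3/4 | worsens further | counted | counted |
| 3/0/3 | normal at rescue, then abnormal | missed | counted |
| 0/3/0 | resolved by rescue | not counted, if the window opens at rescue | not counted |

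The last row depends on the unstated start of the window. If post-baseline is read literally, with no lower limit, 0/3/0 is counted as well.

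**3. Size.** The documents give no rate of Grade 3 values before rescue and no rate of persistence. As an assumption only: if 2% to 10% of SA-RES had such a worsening before rescue and 25% to 75% of these persisted, the share counted with no worsening after rescue would run from 0.02 × 0.25 = 0.5% to 0.10 × 0.75 = 7.5% of the set.

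**The case against.** The strongest defence is that a pre-exposure baseline is an explicit and legitimate choice. It shows cumulative drug effect, and a 0/3/3 pattern is correctly labelled as a worsening from before ABBV-154; the SAP does not call it new since rescue. That is true of the label. It does not explain why SA-RES needs a second cumulative summary when SA-ALL154 supplies one, or why its adverse events start elsewhere.

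Several limits stand:

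- Protocol Table 3 requires interruption of study drug for specified confirmed neutrophil, lymphocyte, platelet, ALT/AST and creatinine abnormalities. This restricts some persistence into rescue. Glucose and potassium are not in that table.
- The liver rows in SAP 10.3 use multiples of ULN without comparison to a baseline value, so a reset does not change them; only the start of the window can.
- The vital-sign criteria for potentially important values are in the product safety SAP, which is not available here. Only the vital-sign change summaries can be criticised.
- Rescue requires symptoms plus an objective marker of inflammation (Protocol 5.4). The last pre-rescue value will often be a flare value, and change from it will include recovery and regression to the mean.

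A reader might infer that the same rule distorts the Re-Induction and Maintenance sets. The documents do not support that as a request for change. Subjects on placebo in Induction already have a baseline at the start of the next period, and among re-randomised Maintenance subjects the common rule applies to all arms, so it creates no expected bias between them.

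**Conclusion.** The mismatch is real and confined to SA-RES. It affects laboratory change, laboratory shift tables, the Grade 3 or higher worsening count, and vital-sign change. It runs in both directions: persisting or improving abnormalities are counted, and recurrences after a normal pre-rescue value are missed. The primary efficacy result is untouched. The distances of 4 to 62 weeks follow from the planned schedule; the frequency of miscounting does not follow from anything in the documents.

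Three stronger readings go too far:

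- Not every pre-rescue abnormality is counted as arising after rescue. If the window opens at rescue, only those still present afterwards are.
- Within-subject laboratory change is not the only evidence on rescue. SA-RES also has adverse-event summaries from the first rescue dose, and subject-level laboratory listings are planned.
- No gain in precision can be claimed for the reset, because the documents give no within-subject correlations.

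The change is worth making because it is cheap and uses data already scheduled.

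**What to change.** In SAP 10.1, add two statements for SA-RES:

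1. For laboratory and vital-sign change, laboratory shift tables and potentially clinically significant laboratory values, baseline is the last value recorded before the first rescue dose.
2. The laboratory and vital-sign window opens at that dose.

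Keep the pre-ABBV-154 baseline for SA-ALL154 and the combined sets. No change is asked for SA2 or SA3.

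The cost is two sentences and one derivation flag. Laboratory and vital-sign visits during Maintenance are already in the activity schedule (Protocol Appendix D), so no new data are needed. The downside is that SA-RES tables would no longer show cumulative change since first exposure, which remains in SA-ALL154. A footnote should say that the pre-rescue value may reflect the flare, and that the set covers the IV rescue dose together with the SC dosing that follows, so the change cannot be read as the effect of the infusion alone.

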10.2 Adverse Events

AEs will be summarized and presented using primary MedDRA SOCs and PTs according to the version of the MedDRA coding dictionary used for the study at the time of database lock. The actual version of the MedDRA coding dictionary used will be noted in the AE tables and in the clinical study report. Specific AEs will be counted once for each subject for calculating percentages, unless stated otherwise. In addition, if the same adverse event occurs multiple times within a subject, the highest severity and level of relationship to investigational product will be reported.

10.2.1 Treatment-Emergent Adverse Events

Induction Period (SA1 population): TEAEs for the Induction Period are defined as events that begin either on or after the first dose of the study drug in the Induction Period and until (i) the first dose of study drug in the Re-Induction Period (if applicable), or (ii) until first dose of study drug in the Maintenance Period (if applicable), or (iii) within 70 days after the last dose administration of the study drug in the Induction Period, whichever is earlier.

Re-Induction Period (SA2 population): TEAEs for the Re-Induction Period are defined as events that begin either on or after the first dose of the study drug in the Re-Induction Period and until (i) first dose of study drug in the Maintenance Period (if applicable), or (ii) within 70 days after the last dose administration of the study drug in the Re-Induction Period, whichever is earlier.

Maintenance Period (SA3 population): TEAEs for the Maintenance Period are defined as events that begin either on or after the first dose of the study drug in the Maintenance Period and until (i) within 70 days after the last dose administration of the blinded study drug in the Maintenance Period, or (ii) initiation of ABBV-154 rescue therapy, whichever is earlier.

ABBV-154 Rescue Therapy (SA-RES population): TEAEs for the ABBV-154 rescue therapy are defined as events that begin either on or after the first dose of the ABBV-154 rescue therapy in the Maintenance Period and until 70 days after the last dose administration of the study drug in the Maintenance Period.

All ABBV-154 (SA-ALL154 population): TEAEs for "All ABBV-154" are defined as events that begin either on or after the first dose of ABBV-154 and within 70 days after the last dose of ABBV-154 in the study. Events that begin when subjects on Placebo will be not included.

Safety analyses from combined periods:

Induction Period + Re-Induction Period ABBV-154 (SA-IN2 population): TEAEs for "Induction Period + Re-Induction Period ABBV-154" (SA_IN2) are defined as events that begin either on or after the first dose of ABBV-154 in the Induction Period and until (i) first dose of study drug in the Maintenance Period (if applicable), or (ii) within 70 days after the last dose of study drug in the study, whichever is earlier.

Induction Period/Re-Induction Period + Maintenance Period ABBV-154 (SA-INMN population): TEAEs for "Induction Period/Re-Induction Period + Maintenance Period ABBV-154" (SA_INMN) are defined as events that begin either on or after the first dose of ABBV-154 in the Induction Period/Re-Induction Period and until (i) within 70 days after the last dose of study drug in the study, or (ii) initiation of ABBV-154 rescue therapy, whichever is earlier.

Induction Period + Re-Induction Period + Maintenance Period ABBV-154 (SA-IN2MN population): TEAEs for "Induction Period + Re-Induction Period + Maintenance Period ABBV-154" (SA-IN2MN) are defined as events that begin either on or after the first dose of ABBV-154 in the Induction Period and until (i) within 70 days after the last dose of study drug in the study, or (ii) initiation of ABBV-154 rescue therapy, whichever is earlier.

If an incomplete onset date was collected for an adverse event, the event will be assumed to be treatment-emergent unless there is other evidence that confirms that the event was not treatment-emergent (e.g., the event end date was prior to the study drug start date). The number and percentage of subjects experiencing treatment-emergent AEs will be summarized.

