Subjects who receive Rescue Therapy, fail to complete glucocorticoid tapering by Week 6, or increase doses of or initiate treatment with aminosaliclates or immunomodulators in the Induction Period will be considered non-responders, regardless of clinical response or endoscopic response (per local read) per the definitions above at Week 12 and will be re-randomized in a 1:1 ratio into 2 ABBV-154 treatment groups in the 12-Week Re-Induction Period as follows:

1. Re-Induction Group 1: Loading dose of 300 mg IV at Week 0, followed by 230 mg SC at Week 2 and EOW;
2. Re-Induction Group 2: Loading dose of 600 mg IV at Week 0, followed by 530 mg SC at Week 2 and EOW.

Subjects who achieve clinical response AND/OR endoscopic response (per local read) at Week 12 of the Re-Induction Period will be re-randomized into the Maintenance Period as described above for subjects achieving clinical response AND/OR endoscopic response (per local read) after Week 12 of the Induction Period. Subjects who do not achieve either clinical response or endoscopic response (per local read) after the Re-Induction Period will be discontinued and will have a follow-up visit scheduled 70 days after last study drug administration.

To determine endoscopic response status for re-randomization into the Maintenance Period, the SES-CD score per local read at Week 12 of the Induction/Re-Induction Period and the SES-CD score per central read at Baseline will be used. In the case of missing data where either clinical response or endoscopic response cannot be determined, subjects will be considered non-responders for the re-randomization criteria evaluation.

Subjects who have an inadequate response at or after Week 4 in the Maintenance Period will be eligible to receive Rescue Therapy with a single dose of ABBV-154 600 mg IV followed by ABBV-154 230 mg SC EOW. Subjects who have received rescue therapy with ABBV-154 for at least 4 weeks and who continue to demonstrate inadequate response may receive additional Rescue Therapy with oral glucocorticoids, aminosaliclates, or immunomodulators. Rescue Therapy options for the Maintenance Period are further described in Section 5.4.

The last dose of study drug will be given at Week 38 of the Maintenance Period. A follow-up visit will be scheduled 70 days after the last study drug administration.

[figure not shown]

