5.8 Randomization/Drug Assignment

All subjects will be assigned a unique identification number by the IRT at the screening visit. For subjects who rescreen, the screening number assigned by the IRT at the initial screening visit should be used. The IRT will assign a randomization number that will encode the subject's treatment group

assignment according to the randomization schedule. Randomization into the 12-Week Double-Blind Induction Period, the 12-Week Double-Blind Re-Induction Period, and the 40-Week Double-Blind Maintenance Period is outlined in Section 4.1.

Randomization at Baseline (Week 0, Day 1) of the Induction Period will be stratified as follows:

- Baseline glucocorticoid use (yes/no);
- Endoscopic disease severity (SES-CD < 15; SES-CD ≥ 15); and
- Inadequate response to adalimumab (yes/no).

Re-randomization at Baseline (Week 0, Day 1) of the Re-Induction Period will be stratified as follows:

- Treatment group in the Induction Period

Re-randomization at Baseline (Week 0, Day 1) of the Maintenance Period will be stratified as follows:

- Achievement of CR100 at entry of the Maintenance Period (Week 12 of the Induction/Re-Induction Period)
- For subjects who enter from the Induction Period: ABBV-154 dose groups in the Induction Period
- For subjects who enter from Re-Induction Period:
 - ABBV-154 dose groups in the Re-Induction Period
 - Induction Period treatment: ABBV-154 (any dose group) versus placebo

All AbbVie personnel with direct oversight of the conduct and management of the trial (with the exception of AbbVie Drug Supply Management Team) will remain blinded to each subject's treatment-assignment in each study period until the Primary Analysis of the respective period. The investigator, study site personnel, and the subject will remain blinded to each subject's assignment throughout the study. Selected AbbVie personnel may be unblinded to treatment assignment after an interim analysis to support regulatory interactions; details will be included in the interim unblinding plan (IUP). To maintain the blind, the ABBV-154 and placebo PFS and vials provided for the study will be identical in appearance. The IRT will provide access to unblinded subject treatment information in the case of a medical emergency.

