Blood samples for conjugated ADC (serum), total antibody (serum), free A-1677770 (plasma) assays							✓	✓	✓
Blood samples for ADA Assay (serum) including ADA titer and nAb assays (Central Lab shipping and lab handling)							✓	✓	✓
Blood sample for bone biomarkers P1NP, OC and CTX			✓				✓		
Blood sample for free and total cortisol (serum)			✓		✓		✓	✓	✓
Blood sample for ACTH			✓		✓		✓	✓	✓
Optional Biomarker sample: Whole Blood Plasma/serum proteomic			✓				✓		
Optional biomarker sample: Whole Blood Peripheral Blood Mononuclear Cells			✓				✓		

Activity	Visit Re-Induction (Week)							Premature Discontinuation	Follow-up 70-Day Visit
	Baseline (Week 0, Day 1)	2	4	6	8	10	12		
Optional biomarker sample: Whole Blood RNA			✓				✓		
Optional biomarker sample: Whole Blood DNA			✓				✓		
Rx TREATMENT									
Assign Study Drug	✓								
Administer Study Drug	✓	✓	✓	✓	✓	✓			
Dispense Study Drug	✓	✓	✓	✓	✓	✓			
Automatic determination of eligibility for the Maintenance Period in EDC							✓		

ACTH = adrenocorticotrophic hormone; ADA = anti-drug antibody; ADC = antibody-drug conjugate; CDAI = Crohn's Disease Activity Index; CTX = C-terminal telopeptide of type 1 collagen; DNA = deoxyribonucleic acid; ECG = electrocardiogram; EDC = electronic data capture; FACIT-Fatigue = Functional Assessment of Chronic Illness Therapy-Fatigue; FCP = Fecal calprotectin; HbA1c = Hemoglobin A1c; HBV = hepatitis b virus; HCV = hepatitis C virus; hs-CRP = high sensitivity C-reactive protein; IBDQ = Inflammatory Bowel Disease Questionnaire; nAb = neutralizing antibody; OC = osteocalcin; P1NP = procollagen type I N-propeptide; PGIC-CD+ = Patient Global Impression of Change – Crohn's Disease+; PGIS-CD+ = Patient Global Impression of Severity – Crohn's Disease+; RNA = ribonucleic acid; SF-36 = Short Form-36

40-Week Maintenance Period

Activity	Baseline (Week 0, Day 1)	Maintenance Period (Week)																			Premature Discontinuation	Follow-up 70- Day Visit
		2	4	6	8	10	12	14	16	18	20	22	24	26	28	30	32	34	36	38		
INTERVIEWS AND QUESTIONNAIRES																						
Adverse Event Assessment		✓	✓	✓	✓	✓	✓	✓	✓	✓	✓	✓	✓	✓	✓	✓	✓	✓	✓	✓	✓	
Record concomitant medication/therapy		✓	✓	✓	✓	✓	✓	✓	✓	✓	✓	✓	✓	✓	✓	✓	✓	✓	✓	✓	✓	
TB risk assessment questionnaire																				✓		
SF-36				✓				✓				✓				✓				✓	✓	
IBDQ				✓				✓				✓				✓				✓	✓	
FACIT-Fatigue				✓				✓				✓				✓				✓	✓	
PGIC-CD+				✓				✓				✓				✓				✓	✓	
PGIS-CD+				✓				✓				✓				✓				✓	✓	

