10.2.4 Treatment-Emergent Adverse Events per Patient-Years of Exposure

TEAEs will be summarized by event rate per 100 subject years, defined as

$$100 \times \frac{\text{Number of TEAEs}}{\text{Total Patient Years}}$$

where total patient years is defined as the sum of the study drug exposure of all subjects, normalized by 365.25, and rounded to 1 decimal place. Note that one event per preferred term per day per subject will be counted in the calculation of the number of AEs (i.e., a preferred term will not be counted twice on the same day for the same subject).

The TEAE rates per 100 patient-years of exposure will be provided for each AE category in the AE overview summary (defined in Section 10.2.2) and for TEAE summary by SOC and PT.

The study drug exposure for each safety population is defined as last dose date plus 70 days, minus the first dose date. For SA-All154 safety population, the duration when subjects on Placebo will not be included in the calculation.

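### In Re-Induction the adverse-event window depends on response (about 84 days for responders, 140 for non-responders), so unequal response between the 230 mg and 530 mg arms gives them unequal event time

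*SAP*

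**What the plan says.** **Design.** Protocol 4.1 has Induction non-responders "re-randomized in a 1:1 ratio into 2 ABBV-154 treatment groups in the 12-Week Re-Induction Period as follows": 300 mg IV then 230 mg SC, or 600 mg IV then 530 mg SC, both every other week. Responders at Week 12 of Re-Induction are re-randomised into Maintenance. For the rest, Protocol 4.1 states: "Subjects who do not achieve either clinical response or endoscopic response (per local read) after the Re-Induction Period will be discontinued", with a follow-up visit 70 days after the last dose. Protocol 6.1 collects adverse events for 70 days after study drug is stopped, so the late events in non-responders are recorded.

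**Event window.** For SA2, SAP 10.2.1 counts events from the first Re-Induction dose "until (i) first dose of study drug in the Maintenance Period (if applicable), or (ii) within 70 days after the last dose administration" of Re-Induction study drug, whichever is earlier. SA-IN2, the combined Induction and Re-Induction population, has the same kind of cut-off.

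**Reporting.** SAP 10.1 tabulates these events by treatment group for SA2. SAP 10.2.2 gives numbers and percentages of subjects, and 10.2.4 gives rates per 100 patient-years. For the rate denominator, 10.2.4 says: "The study drug exposure for each safety population is defined as last dose date plus 70 days, minus the first dose date". It does not cut person-time at the first dose of the next period. The SAP describes no common-window or time-at-risk analysis for SA2.

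**The concern.** Response at Week 12 of Re-Induction is a post-randomisation outcome that the two doses may affect differently, and it sets how long a subject's events are counted. A responder's window closes when Maintenance dosing starts. A non-responder has no Maintenance dose, so the first limb of the rule never applies and the window runs on after the last dose. The two randomised arms are therefore observed for different average times whenever their response rates differ.

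Induction does not have this problem among completers who continue, because responders and non-responders both move to another dosed period at Week 12.

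The additional time is also different in kind. It falls after the last Re-Induction dose, when disease activity or other therapy may contribute events. What is at stake is whether the SA2 columns for the two regimens can be read side by side as a comparison of harm.

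**Working it through.** **Inputs**

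- Period lengths of 12, 12 and 40 weeks (Protocol 4.1).
- Last Re-Induction dose at Week 10: the Appendix D row "Administer Study Drug" is ticked at Weeks 0, 2, 4, 6, 8 and 10, and not at Week 12.
- First Maintenance dose at Maintenance Week 0 (Appendix D), which is Week 12 of Re-Induction (Protocol 5.8).
- Re-Induction response rates: not in the documents, so assumed below.

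**The plan's own figure.** 12×7 + 12×7 + 40×7 = 84 + 84 + 280 = 448 days. This matches the maximum treatment duration in the Protocol synopsis and confirms that Maintenance follows Re-Induction without a gap.

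**Windows for subjects who take every dose**

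- Responder: min(84, 70 + 70) = 84 days (12 weeks).
- Non-responder: 70 + 70 = 140 days (20 weeks).
- Ratio: 140/84 = 1.67.

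**Arm averages.** With r the share entering Maintenance, the mean window is 84r + 140(1 − r) = 140 − 56r days.

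**Crude incidence.** Take a constant hazard with 30% incidence over 140 days. Incidence by Day 84 is 1 − 0.70^(84/140) = 19.3%. Arm incidence is then 19.3r + 30(1 − r), in percent.

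**SAP 10.2.4 rate.** Every completer has a 140-day denominator. A responder's rate is scaled by 84/140 = 0.60 and a non-responder's by 140/140 = 1. For a true rate of 50 per 100 patient-years in both arms, the reported rate is 50 × (140 − 56r)/140.

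| Assumed response, 230 vs 530 mg | Mean window (days) | Difference | Crude incidence | Rate per 100 PY as written |
|---|---|---|---|---|
| 40% vs 40% | 117.6 vs 117.6 | 0 | 25.7% vs 25.7% | 42.0 vs 42.0 |
| 30% vs 40% | 123.2 vs 117.6 | −4.5% | 26.8% vs 25.7% | 44.0 vs 42.0 |
| 40% vs 50% | 117.6 vs 112.0 | −4.8% | 25.7% vs 24.6% | 42.0 vs 40.0 |
| 37% vs 50% | 119.3 vs 112.0 | −6.1% | 26.0% vs 24.6% | 42.6 vs 40.0 |

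At 50% incidence over 140 days, the last row becomes 44.1% vs 42.0%.

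**Why a gap of this order.** The footnote to SAP Table 3 assumes that the two regimens reach 50% and 95% of maximum efficacy. If the 26-point planning difference is taken as the 530 mg effect, the implied gap between doses is 26/0.95 × 0.45 = 12.3 points. This is only a guide: the planning figure is for endoscopic response against placebo in Induction, not for the Re-Induction response criterion.

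**After the change.** With a common Day 84 cut, completers in both arms have 84 days whatever r is, so the event-time ratio is 1.00. If person-time ends with each subject's event window, responders have 84/84 and non-responders 140/140. The rate ratio is then 1.00 under a constant hazard, but crude percentages over the full windows remain unequal.

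**The case against.** The strongest case on the other side concerns consequence and size.

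- **Dose selection.** A reader might infer that the rule makes 530 mg look safer and tilts Phase 3 dose choice towards it. The documents do not support that. Induction Groups 2 and 3 compare the same two regimens, about 53 subjects each, with matched completer windows. Protocol 4.2 ties Phase 3 induction dose selection to the induction regimens and gives Re-Induction the purpose of recapturing non-responders. This objection stands.
- **A larger gap.** A reader might also add the 26-point planning difference to 37%, reach 63% at 530 mg, and find a mean window 12% shorter. That treats a drug-versus-placebo endoscopic difference as a gap between two active doses, on a criterion that also admits clinical response. It is not a supported input.
- **No formal comparison.** The definition of Group 2 versus Group 1 in SAP 9.1 is confined to the efficacy section. The adverse-event tables are descriptive, and Type I error control is not planned. Random error is also larger than the bias: if all 265 subjects entered Re-Induction, an unrealistic maximum of 132.5 per arm, the standard error of 26.0% minus 24.6% would be √[(0.26×0.74 + 0.246×0.754)/132.5], about 5.3 points. This limits the importance, but the shift remains systematic.
- **Direction.** It depends on unequal response and on events continuing at a similar rate off drug; the off-drug rate could be lower or higher. Early stoppers have windows from 70 days (Week 0 dose only) upwards, so unequal discontinuation could add to or offset the imbalance. This stands as a qualifier.
- **Value of the late events.** Protocol 7.7 defines treatment emergence to 70 days after the last dose. Protocol 6.2 warns that adrenal insufficiency may persist for months, and SAP Appendix G lists it as an event of special interest. Removing these events from the main tables would be a real loss, so they should stay there.
- **Laboratory and vital signs.** At-visit changes from baseline do not depend on window length. Worst-value, shift and threshold summaries can.

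**Conclusion.** The point holds in a limited form. Among subjects completing Re-Induction dosing, the SA2 window is about 84 days for responders and about 140 for non-responders. An arm with more responders therefore has less event time, and neither planned summary corrects for it.

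For an assumed response gap of 10 to 13 points, the mean window is about 5% to 6% shorter. Crude incidence shifts by about 1 to 1.5 points, given a constant hazard and 30% incidence over 140 days. The reported rate ratio is about 0.94 to 0.95 when the true rates are equal. With equal response there is no bias. The response rates and the constant hazard are assumptions, and 84 and 140 days are nominal values for full dosing.

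The effect is confined to the descriptive Re-Induction tables and to SA-IN2. It will show in full only at the final analysis, because some follow-up between Weeks 12 and 20 may be missing when Re-Induction is first analysed.

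**What to change.** In SAP 10.2.1, 10.2.4, 10.3 and 10.4:

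1. Keep the 70-day window for the main SA2 tables, in line with Protocol 7.7.
2. Add a between-arm SA2 table of treatment-emergent events and events of special interest with a common window: from the first Re-Induction dose to the earliest of the first Maintenance dose, Day 84, or 70 days after the last dose. Show later events in non-responders separately. Only subjects who stop after the Week 0 dose would then have less than 84 days (70).
3. End each subject's SA2 person-time where that subject's event window ends, in the main and the common-window tables alike.
4. Apply the common cut to SA2 worst-value, shift and potentially clinically significant laboratory and vital-sign summaries. Leave at-visit changes from baseline as they are.
5. State in SA-IN2 outputs that the window length depends on entry to Maintenance.

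The cost is SAP wording, some reprogramming of the affected summaries, and one extra adverse-event table. No data are lost, and trial conduct does not change.
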